6.4 STUDY INTERVENTION COMPLIANCE

Study drug counts will be conducted at all study visits. Per protocol cohorts include 80% compliance with the once daily intervention. A total of 91 tablets will be provided at each study visit. A count of unused medications at the 12 and 24-week follow-up visit will be logged in a drug accountability log and used to determine compliance with the intervention.

6.5 CONCOMITANT THERAPY

For this protocol, a prescription medication is defined as a medication that can be prescribed only by a properly authorized/licensed clinician. Medications to be reported in the Case Report Form (CRF) are concomitant prescription medications, over-the-counter medications and supplements.

Participants are prohibited to take H2 receptor antagonists during the trial.

Research pharmacists will review the study participant's medications listed in their medical record and advise them about the timing of administration of their current medications with famotidine and the acid reflux concomitant medications provided. This will occur at the initial visit and as needed for any follow-up visits that have any new medications added between the visits.

According to pharmacokinetic analyses, single doses of famotidine 20mg raised intragastric pH to mean values of 5.0 (similar for when doses were given in the evening or after breakfast). There were no cumulative effects with repeated doses. However, there are many studies that have shown tachyphylaxis with repeated doses of H2RAs occurring after approximately a week of therapy. Repeated doses of H2RAs are associated with decreased time of gastric pH maintained above 4.0.

The impact on the availability of pulmonary vasodilators is as follows:

- Sildenafil: no interaction known; delayed rate of absorption with high-fat meals but not antacids (time delay 1 hr, reduced maximum concentration by 29%)
- Tadalafil: no significant interaction known; antacids reduced rates of absorption with no change in overall exposure; no significant effects observed with the co-administration of nizatidine 300mg
- Riociguat: no information available specifically with H2RAs; however, concurrent use with antacids is associated with up to 50% reduction in riociguat maximum serum concentration and 25% reduction in exposure; recommended to separate the administration of antacids and riociguat by at least 1 hr; specific mechanisms for these interactions are unknown but riociguat solubility is pH-dependent, and therefore, increases in gastric pH may be partially responsible
- Bosentan: no interaction
- Ambrisentan: no interaction
- Macitentan: no interaction
- Oral treprostinil: no interaction; bioavailability is increased by high fat, high calorie meals by up to 49% but not known to be impacted by acid suppression
- Selexipag: no interaction; time to peak concentration may be delayed with food but not known to be impacted by acid suppression.

References:

Famotidine [package insert]. Morgantown, WV: Mylan Pharmaceuticals Inc.; 2018.

Adempas (riociguat) [package insert]. Whippany, NJ: Bayer HealthCare Pharmaceuticals Inc., 2013.

Interactions. Lexicomp. Wolters Kluwer Health, Inc. Riverwoods, IL. Available at: <http://online.lexi.com>. Accessed March 2019.

6.5.1 RESCUE MEDICINE

Not applicable.

7 STUDY INTERVENTION DISCONTINUATION AND PARTICIPANT DISCONTINUATION/WITHDRAWAL

7.1 PARTICIPANT DISCONTINUATION/WITHDRAWAL FROM THE STUDY

Participants are free to withdraw from participation in the study at any time upon request.

An investigator may discontinue or withdraw a participant from the study for the following reasons:

- Pregnancy
- Serious Adverse event(s) related to the trial medication
- Any relevant deterioration in the health of the subject (AEs, vital signs, laboratory parameters).
- Protocol violation
- Subject's inability to stay on the study drug or off other H2 blockers
- Subject withdrew consent

The reason for participant discontinuation or withdrawal from the study will be recorded on the Case Report Form (CRF).

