5.5 STRATEGIES FOR RECRUITMENT AND RETENTION

All potential subjects for the REHAB-PH Trial will be recruited from the University of Washington Pulmonary Vascular Disease Program.

Potential participants seen in the UW Pulmonary Vascular Disease Clinic will be pre-screened using the electronic medical record. Potentially eligible participants will be recruited at the time of their clinic visit or if time permits, they will receive a one page letter via mail describing the study and/or a phone call from the study coordinator in anticipation of their next visit to clinic. During the potential participant's clinic visit, they will be approached and invited to participate in the REHAB-PH study by the study team at the UW Pulmonary Vascular Disease Clinic. A research coordinator will follow-up with any patient who is willing or considering participation in the study. This may include scheduling a baseline visit in-person at the clinic visit and/or following up by telephone.

Retention is a vital consideration for the success of the study. As we have done in other studies, we will maximize retention by careful training of clinical research staff on best practices for retaining participants. Staff conducting adherence and retention efforts will be trained to conduct effective informed consent to assure that participants fully understand the demands and nature of the study before they enroll. Clinical center staff will carefully review study requirements with the subjects, explain the concept of random assignment and what each treatment involves, and stress the importance of follow-up assessment even if they are not adhering to their assigned treatment. Participants will be nominally remunerated for their participation to offset travel and parking costs. Clinic staff will, at each visit, convey our appreciation for their participation in the study. Concerns about individual participants

will be raised with direct involvement, such as phone calls, by the PI and study center staff as needed to facilitate retention.

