9.4.4 SAFETY ANALYSES

All reported (S)AEs will be coded using MedDRA and grouped by body system. (S)AEs will be tabulated by treatment group using standard coding terms. Incidence of AEs by treatment arm will be tabulated by seriousness, severity, and relationship to study drug. If an AE is reported more than once for a given subject, the greatest severity and the worst-case relationship will be presented in tables. The number of SAEs and AEs will be summarized for each treatment group as follows: (i) The proportion of subjects with at least one (S)AE, (ii) The average number of (S)AEs per subject, and (iii) The rate of (S)AEs per

subject week of follow-up. Histograms showing the frequency of the number of (S)AEs in each treatment group will be included. Rates of (S)AEs by System Organ Class (SOC) will be presented by treatment group. Poisson regression modeling will be used to derive rate ratios and 95% CIs for each SOC. Rate ratios will be compared using a two-sided 0.05 level test for Poisson count data.

Safety lab data at each study visit and changes from baseline will be summarized by treatment group. In addition, clinical laboratory summaries will be presented by treatment group including: (i) incidence of significant abnormalities by visit; (ii) tables summarizing the frequencies of subjects below, within, and above the normal reference ranges at baseline and end of study; and (iii) tables displaying baseline to end of study shifts in each laboratory value (shifts between below, within or above normal range).

Although drug discontinuation is anticipated to be infrequent, the proportion of subjects permanently discontinuing study drug will be tabulated by treatment group. Drug discontinuation events will be categorized as: (1) Permanently discontinued study drug and (2) Permanently discontinued study drug and withdrew from study. The reason for permanent drug discontinuation will be summarized. The number of hospitalization events and proportion of subjects hospitalized from baseline to study termination will be summarized and compared by treatment group. Poisson regression modeling will be used to derive rate ratios and 95% CIs to compare hospitalization rates between treatment groups.

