4 ANALYSIS SETS

4.1 Analysis Set Definitions

The following Analysis sets will be evaluated and used for presentation and analysis of the data:

- **Screening Analysis Set:** Includes all subjects who signed the informed consent form.
- **Enrolled Analysis Set:** Includes all subjects in the Screening Analysis Set who were assigned a randomized treatment.
- **Full Analysis Set (FAS):** Includes all randomized subjects who received at least 1 dose of study medication. Subjects will be analyzed according to their randomized treatment.
- **Per Protocol (PP) Set 1 (PPS1):** Includes all subjects in the FAS whose famotidine medication reconciliation suggest adherence to study drug for 80% or more of administered doses. Subjects will be analyzed according to their randomized treatment.
- **Per Protocol (PP) Set 2 (PPS2):** Includes all subjects in the FAS who (1) were randomized to famotidine for whom H₂ receptor antagonists are detected by mass spectrometry at the final visit and (2) those randomized to placebo for whom H₂ receptor antagonists are not detected at the final visit. Subjects will be analyzed according to their randomized treatment.
- **Safety Analysis Set (SAF):** Includes all randomized subjects who received at least 1 dose of study medication. Subjects will be analyzed according to their actual treatment. Actual treatment is defined as the treatment received for most of the days during the treatment phase of the study.

Per ICH-E9 [1] and ICH-E9-R1 [2] guidelines, will use FAS instead of intention-to-treat. The FAS will be the primary analysis set for the analysis of the primary and secondary efficacy endpoints.

The PPS1 and PPS2 will be used in the sensitivity analyses of the primary and secondary efficacy endpoints.

The SAF will be the primary set for the analysis of the safety parameters.

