5.4 Withdrawals, Dropouts, Loss to Follow-up

Discontinued subjects will not be replaced whether they received or did not receive the study drug. The multiple imputation approach is included in Section 6.4.

Follow-up of subjects who discontinued the study drug early will continue until Week 24 and the study procedures will be assessed as per the schedule of assessment (see Table 9-1).

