6.4.1 Primary efficacy analysis

The primary endpoint is the difference between treatment groups in the change of 6-minute walk distance (6MWD) between baseline and 24 weeks. Linear regression will be performed for the FAS with the change in 6MWD between baseline and 24 weeks as outcome and treatment group as the primary predictor of interest, adjusted for baseline 6MWD and baseline NYHA functional class as the stratification variable. The estimate of the treatment effect will be provided with associated 95% confidence interval (CI).

Missing 6MWD at 24 weeks will be imputed as follows. Subjects known to be dead before the 24 week assessment will have zero imputed for their 24 week 6MWD. Missing 24 week 6MWD for subjects who are alive will be imputed using multiple imputation. The imputation model will have prognostic variables as the predictor variables. Prognostic variables will include age, gender, and etiology of pulmonary hypertension, baseline six minute walk test distance, baseline right ventricular diameter, and baseline BNP. The multiple imputation will use Markov Chain Monte Carlo (MCMC), which assumes that the variables in the imputation model have a joint multivariate normal distribution (MVN). The number of imputations to be performed will be 100. One hundred is selected because it is not too large that it requires heavy computations

and is not too small (such that the Monte Carlo error is still small enough at around 0.1 times the standard deviation). The “proc mi” procedure in SAS will be used to impute the missing observations.

PAH etiology in the analysis will be as follows:

- Idiopathic
- Familial
- Congenital Heart Disease
- Collagen Vascular Disease
- Toxin
- Portopulmonary Hypertension

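### Protocol 7.1 allows withdrawal from the study for failing to stay on drug, while SAP 5.4 has drug-stoppers followed to Week 24; using that discretion leaves avoidable gaps in the primary endpoint.

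*Protocol*

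**What the plan says.** The heading of Protocol Section 7 covers both stopping the intervention and leaving the study, but 7.1 deals only with leaving the study. It opens "An investigator may discontinue or withdraw a participant from the study for the following reasons", and one listed reason is "Subject's inability to stay on the study drug or off other H2 blockers". Nothing in Section 7 describes a participant who stops drug and stays in follow-up.

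Other places do describe that participant:

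- SAP 5.4: "Follow-up of subjects who discontinued the study drug early will continue until Week 24", with procedures done as scheduled.
- Protocol 5.5: staff are to "stress the importance of follow-up assessment even if they are not adhering to their assigned treatment".
- Protocol 9.4.4 sorts drug discontinuations into "1) Permanently discontinued study drug and (2) Permanently discontinued study drug and withdrew from study".

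SAP Section 7, which lists changes from the protocol, does not mention follow-up after stopping drug.

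On the analysis side, SAP 4.1 states: "The FAS will be the primary analysis set for the analysis of the primary and secondary efficacy endpoints". The FAS is everyone randomised who took at least one dose, analysed as randomised. SAP 6.4.1 adds: "Missing 24 week 6MWD for subjects who are alive will be imputed using multiple imputation". The predictors are given as follows: "Prognostic variables will include age, gender, and etiology of pulmonary hypertension, baseline six minute walk test distance, baseline right ventricular diameter, and baseline BNP". Treatment arm, the Week 12 walk, drug stop and reason for withdrawal are not listed. PPS2 (SAP 4.1) is defined by mass spectrometry at the final visit, and Protocol 6.1.1 uses the same end-of-trial assay to judge contamination.

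**The concern.** An analysis of all dosed participants as randomised needs the Week 24 walk from people who stopped drug as well as from those who stayed on it. If a site uses 7.1 to remove someone for non-adherence, that walk is lost through an administrative decision, not through refusal or death. The reason arises after randomisation and may be linked to tolerability or worsening health. The listed imputation predictors cannot see it, so the participant is filled in as if they resembled those who stayed.

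The same bullet covers use of other H2 blockers. Removing those participants before Week 24 also removes the samples that would show contamination. The check in Protocol 6.1.1 could then look cleaner than the trial was, and PPS2 membership could not be determined for them.

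**Working it through.** **1. Do the passages conflict?** Protocol 7.1 gives permission to end participation. SAP 5.4 says follow-up will continue. Protocol 5.5 and 9.4.4 recognise the participant who is off drug but still in the study, but neither limits 7.1. The conflict therefore arises each time the 7.1 permission is used for this reason, and not otherwise.

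**2. Is it a matter of power?** Inputs from SAP 6.1 and 6.2.1: difference 31.9 m, SD 37.6 m, two-sided alpha 0.05, 40 per arm. A two-sample t-test with standardised difference 31.9/37.6 = 0.848 gives power 0.963 at 40 per arm and 0.944 at 36. This reproduces the stated 0.96 and 0.94. At 34 per arm (15% loss) power is 0.931, and at 32 (20% loss) it is 0.916. Lost power is not the main problem. The exposure is bias.

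**3. Size of the bias (assumed inputs).** The documents give no rate of withdrawal under this bullet and no outcome for those withdrawn. Assume k of 40 in one arm are withdrawn and their true Week 24 walk differs from the imputed value by D metres. Then bias = (k/40) × D.

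For scale, the standard error is 37.6 × √(2/40) = 8.4 m. The last two columns hold it at that value, without covariate adjustment or extra imputation variance.

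| k | D (m) | Bias (m) | Two-sided rejection rate if there is no true effect | Power at a true 31.9 m if the bias runs against famotidine |
|---|---|---|---|---|
| 2 | 30 | 1.5 | 0.054 | 0.946 |
| 2 | 100 | 5.0 | 0.091 | 0.885 |
| 4 | 30 | 3.0 | 0.065 | 0.924 |
| 4 | 100 | 10.0 | 0.22 | 0.73 |

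**4. When is it near zero?** With losses in both arms, the net bias is the difference of the two terms. Suppose all benefit is lost off drug, set the placebo change at 0, and impute without treatment arm.

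- 4 of 40 lost in each arm: the imputed change averages 31.9/2 = 15.95 m in both arms. Estimate: (0.9 × 31.9 + 0.1 × 15.95) − 0.1 × 15.95 = 28.7 m. True all-participant difference: 0.9 × 31.9 = 28.7 m. Bias: 0.
- 4 lost, famotidine arm only: the pooled mean is 36 × 31.9/76 = 15.1 m, so the bias is 0.1 × 15.1 = 1.5 m.
- 2 lost, famotidine arm only: the pooled mean is 38 × 31.9/78 = 15.5 m, so the bias is 0.05 × 15.5 = 0.8 m.

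**5. Do the planned sensitivity analyses bracket it?** Complete case drops the same people. Zero imputation is too blunt: at an assumed mean walk of 300 to 450 m, each extra missing walk in one arm of 40 shifts the difference by 300/40 = 7.5 m to 450/40 = 11.25 m. An imbalance of 31.9/11.25 = 2.8 to 31.9/7.5 = 4.3 participants would then offset the whole 31.9 m.

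**The case against.** The strongest reply is that 7.1 is permissive. A site that keeps drug-stoppers in follow-up and rarely uses the discretion complies with every passage. Protocol 5.5, Protocol 9.4.4 and SAP 5.4 together suggest that this is the intent. Protocol 9.4.4 also expects discontinuation to be infrequent, and the power calculation already allows 10% attrition. Even a 3 m bias is under 0.4 of the 8.4 m standard error.

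Most of this stands. A reader might infer that 7.1 and SAP 5.4 cannot both be followed. The documents do not support that: gaps can enter, but they need not, and their number is unknown.

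What does not stand is that the other passages settle the matter. They show the distinction was understood, but a site reading Section 7 would find only the exit from the study.

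The visit windows help only in part. Under SAP 5.5, a withdrawal visit with a walk on Day 126 to 175 counts as Week 24. Neither schedule lists an early-withdrawal visit, although SAP 5.2 names one, and a walk before Day 126 leaves Week 24 empty.

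**Conclusion.** The inconsistency is real and worth removing. Used for non-adherence or H2-blocker use, Protocol 7.1 creates avoidable and plausibly informative gaps in the Week 24 walk and the final mass-spectrometry sample. The bias cannot be fixed from the documents. It is 1.5 to 10 m if 2 to 4 of 40 in one arm are lost and their walks are 30 to 100 m from the imputed values, and it may be near zero if losses balance. Those inputs are assumptions.

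A reader might also infer that imputation would credit drug-stoppers with the full benefit, overstating the effect by 0.05 × 31.9 = 1.6 m to 0.10 × 31.9 = 3.2 m at 5 to 10% loss. That requires treatment arm in the imputation model or imputation within arm, and SAP 6.4.1 lists neither. Under the listed predictors, the same scenario gives 0 to 1.5 m.

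**What to change.** Reconcile Protocol 7.1 with SAP 5.4, Protocol 5.5 and Protocol 9.4.4 by separating two events: stopping study drug and leaving the study. Word 7.1 so that non-adherence or H2-blocker use alone does not end collection of the Week 24 assessments.

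Two limits apply:

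- The clinical and safety grounds in 7.1, and the pregnancy withdrawal rule in Protocol 8.2.8, are for the sponsor to reconcile. A blanket rule that only withdrawn consent ends data collection would clash with 8.2.8.
- Protocol 8.1 requires the Week 24 catheterisation and exercise sub-study tests to be done while on drug, whereas SAP 5.4 points to the whole schedule. The revised text should say how these tests are handled for participants off drug.

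The cost is protocol wording and a modest effort to retain off-drug participants. The Week 24 visit is already scheduled, and the walk is abstracted from routine care (Protocol 1.3). Label: cheap improvement.

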7.2 LOSS TO FOLLOW-UP

A participant will be considered lost to follow-up if he or she fails to return for a scheduled visit and is unable to be contacted by the study site staff.

The following actions must be taken if a participant fails to return to the clinic for a required study visit:

- The site will attempt to contact the participant and reschedule the missed visit within a week and counsel the participant on the importance of maintaining the assigned visit schedule and ascertain if the participant wishes to and/or should continue in the study.
- Before a participant is deemed lost to follow-up, the investigator or designee will make every effort to regain contact with the participant (where possible, 3 telephone calls and, if necessary, a certified letter to the participant's last known mailing address or local equivalent methods). These contact attempts should be documented in the participant's study file.
- Should the participant continue to be unreachable, he or she will be considered to have withdrawn from the study with a primary reason of lost to follow-up.

8 STUDY ASSESSMENTS AND PROCEDURES

8.1 EFFICACY AND SAFETY ASSESSMENTS

At the baseline visit participants will be consented and inclusion and exclusion criteria will be assessed for eligibility. Participants will then undergo a standardized clinical assessment with medical history, symptom assessment including NYHA functional class, vital signs (includes height, blood pressure, heart rate, oxygen saturation), weight, and physical examination. Demographics will be collected. A blood draw will include safety laboratories including comprehensive metabolic panel, complete blood count, BNP, and pregnancy test (for pre-menopausal women). The pregnancy test can be performed as either a blood or urine test. A blood-based pregnancy test is preferred; however, if a urine test is used then it must be performed by study personnel and documented in the medical record. All participants will have serum collected for mass-spectrometry at the end of the study to evaluate for contamination of the study design by individuals taking over-the-counter H2 receptor antagonists. Serum, plasma, and blood

for RNA isolation will be collected and stored for participants. Subjects will have an option to opt-out of this additional research blood sample. All participants will have a transthoracic (TTE) echocardiogram and emPHasis-10 measure of health-related quality of life. They will also complete a 6 minute walk distance (6MWD) at their baseline visit. Distance, BORG dyspnea scores, peak heart rate, oxygen saturation, and heart rate recovery at one minute will be collected to characterize the walk.

Participants who are not participating in the right heart catheterization or exercise sub-studies will be randomized and study drug will be dispensed at this visit. Participants will be instructed to take one tablet daily (20 mg of famotidine or placebo) the following day which will represent day zero and entry into the study. An antacid (Calcium Carbonate) and proton pump inhibitor (Omeprazole), both over-the-counter medications, will be provided by a study physician to participants as needed for short and long term heartburn control in an effort to try and minimize contamination of the study question by inadvertent H2 receptor antagonist use by participants attempting to self-treat heartburn with over-the-counter medications.

Individuals who are participating in the right heart catheterization or exercise sub-studies will be randomized and study drug will be dispensed at their last baseline study assessment. These participants will also be instructed to take one tablet daily (20mg of famotidine or placebo) the day following randomization and dispensing of the study drug.

Regardless of the participation in sub-studies, all baseline assessments need to be completed within 14 days prior to the start of study drug (not inclusive of the date the first dose of study drug is taken). The day study drug is taken will be considered day 0.

Week 4 phone call will be on day 28 ± 7 . This visit will address study drug adherence and adverse events.

Week 12 visit will occur at day 84 ± 7 . This visit will include a standard clinical assessment with a symptom assessment including NYHA Functional Class, vital signs, weight, and physical examination. Participants will also have a 6-minute walk distance, emPHasis-10 score, evaluation for adverse events, evaluation for medication and study drug compliance, and dispensation of study drug. Due to the COVID-19 pandemic, this visit can be done as telehealth or in-person based on current COVID-19 levels in the community and patient preference. If visit is done as telehealth it will include a symptom assessment including NYHA Functional Class, emPHasis-10 score, evaluation for adverse events, and evaluation for medication and study drug compliance. The UWMC Investigational Drug Service will ship the next supply of study medication to the subject via FedEx overnight shipping to coincide with this visit. In person visits will be encouraged.

Week 24 visit will occur at day 168 ± 7 and will include all components included in the baseline visit: a standard clinical assessment with a symptom assessment including NYHA Functional Class, vital signs, weight, and physical examination. Participants will also have a 6-minute walk distance, an echocardiogram, emPHasis-10, evaluation for adverse events, evaluation for medication and study drug compliance, and a blood draw including a comprehensive metabolic panel, complete blood count, BNP,

and pregnancy test if indicated. The pregnancy test can be performed as either a blood or urine test. A blood-based pregnancy test is preferred; however, if a urine test is used then it must be performed by study personnel and documented in the medical record. All participants will have serum collected for mass-spectrometry at the end of the study to evaluate for contamination of the study question by individuals taking over-the-counter H2 receptor antagonists. Serum, plasma, and blood for RNA isolation will be collected and stored for participants.

Adverse events and concomitant medications will be assessed and collected at all visits.

Optional Right Heart Catheterization (RHC) Evaluation: Subjects will have the option to take part in the RHC portion of the study that will be performed within 14 days of the Baseline Visit and within 7 days of the Week 24 Visit. The baseline visit must be done while not taking study drug and the week 24 visit must be done while taking study drug. This is a procedure which is performed for all patients with PAH. The purpose of this optional evaluation is to track changes in the measurements of the subjects' heart and lungs that might be related to study treatment with famotidine. 1% lidocaine local anesthesia will be used. It will take 3-4 hours to complete the right heart catheterization. On the day of the right heart catheterization, subjects will check into the cardiac catheterization laboratory at the University of Washington Medical Center. A nurse will check the subject's vital signs and basic bloodwork to make sure that the procedure is safe to perform. Once this is done, subjects will go into the cardiac catheterization laboratory where [name] will numb the area for the procedure with lidocaine. This will typically be the right side of the neck. After numbing the area, [name] will place a catheter into a vein, the right atria, right ventricle, and pulmonary artery and measure pressures at each position and check to see how much blood the heart is pumping. The process of inserting the catheter and taking measurements normally takes approximately 20-30 minutes. After these measurements, the catheter will be removed, a nurse will hold pressure on the area to ensure that there is no bleeding, and the subject will then be free to go.

Optional Cardiopulmonary Exercise Test (CPET) Evaluation: Subjects will have the option to take part in the CPET portion of the study that will be performed within 14 days of the Baseline Visit and within 7 days of the Week 24 Visit. The baseline visit must be done while not taking study drug and the week 24 visit must be done while taking study drug. CPET will be done via bicycle ergometry and will be performed in the Exercise Testing Laboratory of the UW Lung Function Testing Center. This is a routine clinical test used by pulmonologists and cardiologists, but is not routinely done for all individuals with PAH. This test measures how the body tolerates physical activity. Due to the Covid 19 Pandemic, the Lung Function Testing department at UWMC is requiring Covid testing prior to any procedures done in the lab. As long as this requirement is in place, you will be given a phone number to call to arrange testing at a drive through testing site within 72 hours of your appointment. At the drive through site, you will stay in your car and a nurse will use a nasal swab (like a long Q-tip) inserted into your nose and back of throat to collect cells which will be sent to the lab. You will be notified in the event of a positive test result.

On the day of the test, subjects will check into the Lung Function Testing Center at the University of Washington Medical Center. They should wear clothing suitable for exercise. A respiratory therapist will

check the subject's vital signs and conduct breathing tests. After this they will hook up an EKG, monitor the subject's oxygen via a probe on their finger, and place a neoprene mask over their nose and mouth. These will measure a number of important exercise characteristics. Subjects will then ride a stationary bicycle in the exercise lab. The test is variable in length and designed to push the subject to exercise as hard as they can tolerate in a highly supervised setting. Most participants exercise for 5-15 minutes with increasing resistance on the stationary bicycle. This is followed by a "cool-down" period on the bicycle. When the subject is done, a respiratory therapist will continue to monitor the subject for 5-10 minutes at rest. After this time, subjects will be free to go.

Participants in the invasive hemodynamic and cardiopulmonary exercise testing (CPET) sub-studies will have the option to do both tests on the same day or separate days, but within the 3 days of the final visit.

